## 6.2.1 Adverse Events

Adverse events will be categorized as those which occur prior to first dose or treatment-emergent as follows:

- Adverse events prior to first dose  
Adverse events prior to first dose is an adverse event which starts prior to the first dose of study drug. If the adverse event occurs on Day 1 and the onset check box is marked “Onset before first dose of study drug”, then the adverse event will be considered as an AE prior to first dose. If the adverse event occurs on Day 1 and the onset check box is marked “Onset after first dose of study drug” or the onset check box is left blank, then the adverse event will not be considered as an AE prior to first dose.
- Treatment-emergent adverse events (TEAEs; frequency, severity, seriousness, and relationship to study drug).

TEAE is defined as an adverse event which starts, or worsens, after the first dose of study drug through 30 days after the last dose of study drug. If the adverse event occurs on Day 1 and the onset check box is marked “Onset after first dose of study drug” or the onset check box is left blank, then the adverse event will be considered treatment emergent. If the adverse event occurs on Day 1 and the onset check box is marked “Onset before first dose of study drug”, then the adverse event will not be considered treatment emergent, unless it worsens in severity after Day 1 (up to day 30 after last dose).

TEAE (Treatment period) is an adverse event which starts, or worsens, after the first dose of study drug through to 4 days after the last dose of study drug. If the adverse event occurs on Day 1 and the onset check box is marked “Onset after first dose of study drug” or the onset check box is left blank, then the adverse event will be considered treatment emergent. If the adverse event occurs on Day 1 and the onset check box is marked “Onset before first dose of study drug”, then the adverse event will not be considered treatment emergent, unless it worsens in severity after Day 1 (up to day 4 after last dose).

TEAE (Follow-up period) is an adverse event which starts, or worsens, 5 days after the last dose of study drug through 30 days after the last dose of study drug.

A drug-related TEAE is defined as any TEAE with a possible or probable relationship to study treatment as assessed by the investigator or with missing assessment of the causal relationship.

For each AE, duration will be calculated in days, using the following formula:

- Duration of AE = End date of AE – Start date of AE +1,

where the start date of AE and the end date of AE are defined as the onset date and end date of the AE, as captured in the eCRF. Imputed dates for the start date or end date may be used to calculate duration (Section 7.11.1).

### **6.2.2 Clinical Laboratory Variables**

Clinical laboratory variables are raw values (i.e., values at each scheduled visit) and changes from baseline for chemistry, hematology and urinalysis parameters at Weeks 2, 4, 8 and Week 10.

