During the treatment period, subjects will return to the clinic per schedule for safety and efficacy procedures (see Schedule of Assessments for details). Subjects who do not complete the treatment period will be requested to complete EOT visit procedures.

*Follow-up Period:*

Subjects are encouraged to abstain from any concomitant medications for the treatment of fibromyalgia pain prior to Visit 7/Week 10. Subjects are encouraged to abstain from alcohol. Rescue medication is allowed during the follow-up period. Subjects will continue to enter their daily average pain score (NRS), [REDACTED] and acetaminophen use into their e-diary and return diaries at Visit 7/Week 10. All subjects will return to the site for a follow-up visit at Day 71, 2 weeks following the EOT visit (Day 57). A follow-up safety phone call will take place approximately 4 weeks post study drug discontinuation (Day 85/EOS).

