#### **7.5.3 Clinical Laboratory Evaluation**

The baseline visit is the last measurement taken prior to first dose of study drug.

Quantitative clinical laboratory variables, i.e., hematology & coagulation, and biochemistry will be summarized using mean, SD, minimum, maximum and median for each treatment group at each visit. Additionally, a within-subject change will be calculated as the post-baseline measurement minus the baseline measurement and summarized in the same way. Each laboratory result will be classified as low (L), normal (N), or high (H) at each visit according to the laboratory supplied reference ranges.

The number and percentage of subjects below and above the reference range will be summarized for each treatment group at each visit.

For hematology and biochemistry, two types of shift tables will be presented for each treatment group:

- Shift tables of reference range changes from baseline to post-baseline value at each specified time point (low, normal, high), and
- Summary shifts of reference range changes from baseline to post-baseline value at each specified time point (shift from normal or high to low, shift from normal or low to high, categorized increase [shift from low to normal, low to high or from normal to high], categorized no change [value stays in the same reference range], categorized decrease [shift from high to normal, high to low or from normal to low]).

The following list of parameters will be summarized using descriptive statistics and for the shift table.

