**Table 21      Laboratory Parameters for Descriptive Statistics and Shift Table**

Lab Panel	Analysis Time Point	Parameter
Hematology and Coagulation	Baseline	Hemoglobin Hematocrit
	Treatment period	Erythrocytes (Red blood cell [RBC]) Leukocytes (White blood cell [WBC]) Differential WBC
	Week 2, Week 4, Week 8,	Platelets PT and INR
	Follow-up	MCV MCH
	Week 10	Reticulocytes
Biochemistry	Baseline	Sodium Potassium
	Treatment period	Calcium Chloride
	Week 2, Week 4, Week 8,	Magnesium Glucose
	Follow-up	Creatine Kinase Creatinine
	Week 10	Alkaline Phosphatase (ALP) Lactate dehydrogenase (LDH) Aspartate transaminase (AST) Alanine transaminase (ALT) Gamma glutamyl transpeptidase (GGT) Total bilirubin (direct and indirect) Total protein Albumin Total cholesterol Triglycerides Uric Acid Blood Urea Nitrogen (BUN) Inorganic phosphate

All laboratory measurements, including the derived outcomes (change from baseline and flagging of abnormal value with high and low) will be presented in the listing. Urinalysis will be listed only.

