### **7.5.7 Columbia Suicide Severity Rating Scale**

Number and percentage of subjects in each of the categories of C-SSRS described in Section 6.2.5 will be summarized at each analysis time point (Baseline, Week 2, Week 4, Week 8, EOT and Week 10) by treatment group. For each analysis time point, if a subject answers "yes" to more than one question within a category, the worst finding will be used.

For the overall during the double-blind treatment period and the overall during the follow-up period, a subject's worst finding during that period will be used.

All C-SSRS assessments will be listed only for subjects with at least one event of suicidality (suicidal ideation and/or suicidal behavior).

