**Table 30 Day Windows: Laboratory, Vital Sign Variables and C-SSRS**

Analysis Time Point	Target Day	Visit Window (Day)
Week 2	Study day 15	Study days 2 to 22
Week 4	Study day 29	Study days 23 to 43
Week 8	Study day 57	Study days 44 to 71
EOT a	Not applicable	Study day 2 to Follow-up day 4
Double-blind treatment period b	Not applicable	Study day 2 to Follow-up day 4
Week 10 c	Follow up day 14	Follow-up days 5 to 28
Follow-up period d	Not applicable	Follow-up day 5 onwards

Baseline is defined as the last assessment on or prior to the first dose day (Day 1) of double-blind study drug.

a EOT value is the last available non-missing post-baseline measurement within the visit window. Vital signs will also include Day 1 2 hours post-dose.

bOnly applicable to potentially clinically significant laboratory parameters, potentially clinically significant vital signs, orthostatic outlier vital signs and C-SSRS. Vital signs will also include Day 1 2 hours post-dose.

cOrthostatic vital signs are not captured at Week 10.

dOnly applicable to potentially clinically significant laboratory parameters, potentially clinically significant vital signs and C-SSRS.

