**Table 31 Day Windows: Categorical ECG Assessment**

Analysis Time Point	Target Day	Visit Window (Day)
Week 8	Study day 57	Study days 44 to 71
EOT a	Not applicable	Study day 2 to Follow-up day 4
Double-blind treatment period b	Not applicable	Study day 2 to Follow-up day 4
Week 10	Follow-up day 14	Follow-up days 5 to 28
Follow-up period	Not applicable	Follow-up day 5 onwards

Baseline is defined as the last assessment on or prior to the first dose day (Day 1) of double-blind study drug.

a EOT value is the last available non-missing post-baseline measurement within the visit window.

For safety variables, the following rules will apply:

1. For laboratory and vital sign variables, if a subject has more than one visit with a measurement included within a window, the assessment closest to the target day will be used. In case of ties between observations located on different sides of the scheduled day, the later assessment will be used. In case of ties located on the same side of the target day (i.e., more than one value for the same day), the mean of the values will be used.
2. For the categorical ECG assessment, if a subject has more than one result with a measurement included within a window, the assessment closest to the target day will be used. In case of ties between observations located on different sides of the target day, the later assessment will be used in the analyses. In case of ties located on the same side

of the scheduled day (i.e., more than one value for the same day), the worst-case parameter value (where ‘abnormal – clinically significant’ is considered worse than ‘abnormal – not clinically significant’, which in turn are both considered worse than ‘normal’).

3. For the C-SSRS, if a subject answers ‘yes’ to more than one question within a window, the worst-case response (within a category) will be used irrespective of whether this is closest to the target day.

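### The SAP defines an end-of-treatment value for laboratory tests but no laboratory summary uses it, so some early discontinuers' last on-drug results drop out of the change, out-of-range and shift tables.

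*SAP*

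**What the plan says.** **Collection.** The laboratory table in Protocol 5.4.3 schedules hematology, biochemistry and urinalysis at Week 8/EOT. For early stoppers, Protocol 2.2.1 states: "Subjects who do not complete the treatment period will be requested to complete EOT visit procedures".

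**Definition.** SAP Table 30 is titled "Day Windows: Laboratory, Vital Sign Variables and C-SSRS". It has an EOT row running from Study day 2 to Follow-up day 4, and footnote a reads: "EOT value is the last available non-missing post-baseline measurement within the visit window". No footnote excludes laboratory data. SAP 7.11.5.2 also refers to an EOT time point for safety variables, and bars results taken more than 4 days after the last dose from it.

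**Use.** SAP 6.2.2 specifies "changes from baseline for chemistry, hematology and urinalysis parameters at Weeks 2, 4, 8 and Week 10". Table 21, "Laboratory Parameters for Descriptive Statistics and Shift Table", lists Baseline and Weeks 2, 4, 8 and 10. In SAP 7.5.3 the descriptive, change and out-of-range summaries are by visit, and the shift tables are by specified time point. None names EOT.

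**Other safety data.** The C-SSRS is summarized at "Baseline, Week 2, Week 4, Week 8, EOT and Week 10" (SAP 7.5.7), and the ECG at Baseline, Week 8, EOT and Week 10 (SAP 7.5.5).

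**Selection.** The first safety rule in SAP 7.11.5.3 begins "For laboratory and vital sign variables, if a subject has more than one visit with a measurement included within a window". It then keeps the result closest to the target day, or the later one when two are equally far on opposite sides.

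**The concern.** The plan derives an EOT laboratory value and then calls for it in no laboratory table. This matters because of the selection rule. The Table 30 windows run without a gap from Day 2 to Day 71, so an on-treatment EOT lab always falls in the Week 2, 4 or 8 window. There it may have to compete with a scheduled lab that is nearer the target day. If it loses, the by-visit and shift tables show the earlier result, and nothing tells the reader that a later on-drug result was set aside.

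Safety and tolerability relative to placebo is a primary objective. The results at risk belong to subjects who stopped treatment, and are the ones nearest to stopping. If stopping were related to a laboratory effect of ASP8062, those are the results a reviewer would most want in the shift tables.

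**Working it through.** The plan states no figure on this point, so there is none to reproduce. The check applies its own window rule.

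**Inputs.** Windows and targets from SAP Table 30: Week 2, Days 2-22 (target 15); Week 4, Days 23-43 (target 29); Week 8, Days 44-71 (target 57). Selection rule from SAP 7.11.5.3. Planned randomization of 178 from Protocol 2.2.1. Discontinuation rate and timing are not given and are assumed below.

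**Step 1: visits on target.** Put the Week 2 and Week 4 labs on Days 15 and 29, and an EOT lab on each Day d from 2 to 56. The EOT lab is displaced when an earlier lab in the same window has a smaller distance |day - target|.

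| EOT lab on | Window | Competing lab | Outcome | Days |
|---|---|---|---|---|
| 2-15 | Week 2 | none earlier in window | kept as Week 2 | 14 |
| 16-22 | Week 2 | Day 15, distance 0 | displaced | 7 |
| 23-29 | Week 4 | none earlier in window | kept as Week 4 | 7 |
| 30-43 | Week 4 | Day 29, distance 0 | displaced | 14 |
| 44-56 | Week 8 | none earlier in window | kept as Week 8 | 13 |

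Displaced: 7 + 14 = 21 of 55 days, or 38%. Kept: 34 of 55, or 62%.

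**Step 2: jitter and timing.** Simulation with the scheduled visits moved by up to 2 days either way:

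| Assumed timing of the EOT lab | Share displaced |
|---|---|
| Uniform over Days 2-56 | 34% |
| Exponential, mean 28 days | 28% |
| Exponential, mean 14 days | 19% |
| Exponential, mean 7 days | 8% |
| All on Days 2-14, or all on Days 44-56 | 0% |
| All on Days 32-43 | 100% |

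The exponential times start at Day 2 and are truncated before Day 57.

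**Step 3: number of subjects.** Displaced subjects = 178 x (proportion stopping early) x (share displaced).

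| Stopping early | Subjects | 25% displaced | 38% displaced |
|---|---|---|---|
| 5% | 8.9 | 2.2 | 3.4 |
| 10% | 17.8 | 4.5 | 6.8 |
| 20% | 35.6 | 8.9 | 13.5 |
| 30% | 53.4 | 13.3 | 20.3 |

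This gives about 2 to 20 subjects over both arms. With strongly front-loaded stopping (8% displaced) it falls to 8.9 x 0.08 = 0.7 up to 53.4 x 0.08 = 4.3. Each count assumes that every early stopper attends EOT within 4 days of the last dose, so it is an upper bound for its rate and timing.

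**Step 4: where a displaced result still appears.** The PCS tables (SAP 7.5.3.1 and 7.5.3.2) take the highest or lowest value over the double-blind period, and so include it. The listings flag it if high or low. Many non-liver PCS limits are wide: hemoglobin below 7.0 g/dL, platelets below 40 x10^3/µL, creatinine above 5.00 mg/dL (SAP Appendix 3). Neither Table 22 nor Appendix 3 has a criterion for creatine kinase, GGT, LDH, differential WBC, reticulocytes, albumin, total protein, cholesterol, triglycerides or inorganic phosphate.

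**Step 5: with EOT in the tables.** For EOT labs within 4 days of the last dose, displacement from the summaries falls from 21 of 55 days to 0 of 55.

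**The case against.** **The SAP follows the protocol.** Protocol 2.3.1 lists safety laboratory tests at Weeks 2, 4, 8 and 10, and 6.2.2 repeats that. But the same list gives ECG and C-SSRS without EOT, and the SAP adds EOT to both. Following the protocol therefore does not explain the difference, and the SAP gives no other reason. Vital signs are a weaker comparison, because SAP 7.5.4 uses a combined Week 8/EOT label.

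**Important abnormalities surface elsewhere.** This largely stands. Under Protocol 5.5.1 a laboratory abnormality is an AE if it causes signs or symptoms, needs intervention, requires interruption or discontinuation of study drug, or is clinically significant in the investigator's opinion. Laboratory-driven stopping should therefore appear in the TEAE tables, including those for discontinuation. The PCS tables also catch ALT or AST above 3xULN (a level the protocol calls moderate), ALP above 1.5xULN, total bilirubin above 2xULN and INR above 1.5; the INR criterion partly covers PT. A reader might infer that a displaced result is visible only in a listing. That is true only of a result that meets no PCS criterion and is not reported as an AE.

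**The numbers are soft.** This stands too. The only related figure is the roughly 5% in the Protocol synopsis who will not contribute to the analysis, and that is not a discontinuation rate. EOT attendance is only requested. Labs more than 4 days after the last dose are barred from EOT, and the change proposed here would not recover them; those on Follow-up days 5-28 fall in the Week 10 window.

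**Bias is not shown.** A displaced subject still contributes an on-drug result from the same window, about two weeks earlier at most, and no safety hypothesis is tested. The documents do not show that the earlier result would be the more normal one.

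**Conclusion.** The point holds as an inconsistency with a limited but real consequence. Table 30 defines a laboratory EOT value, SAP 6.2.2, Table 21 and 7.5.3 never use it, and the closest-to-target rule then removes some last on-drug results from every by-visit and shift table. The displaced share depends on assumed stopping times: 38% with even stopping and visits on target, and 8%-34% in the jittered scenarios. The range of about 2-20 subjects further assumes 5%-30% stopping early and 25%-38% displaced.

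Three stronger conclusions might be inferred and are not supported:
- that the plan has no EOT time point for laboratory data, since Table 30 supplies one;
- that many discontinuers are affected, since no document figure supports this and most possible EOT days keep the result;
- that the tables would understate a difference from placebo, which would require stopping related to drug and to laboratory change, with later results worse than earlier ones.

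The gap is confined to moderate changes below the PCS limits, and to analytes with no PCS criterion, where the result is not reported as an AE.

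**What to change.** Add EOT, as Table 30 footnote a already defines it, to SAP 6.2.2 and Table 21. In 7.5.3, produce the baseline-to-EOT change, out-of-range and shift summaries alongside the by-visit ones. If the sponsor prefers not to tabulate EOT for laboratory data, Table 30 should exclude laboratory variables from its EOT row and give the reason; that removes the inconsistency but leaves the displaced results untabulated.

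The cost is a short SAP edit and one extra time point in existing tables. The derivation is already written and no new data are needed.

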### **6.2.3 Vital Signs**

Vital signs variables are raw values (i.e., values at each scheduled visit) and changes from baseline in systolic blood pressure (SBP), diastolic blood pressure (DBP) and pulse rate at Day 1 2-hours post dose, Weeks 2, 4, Week 8/EOT and Week 10. Orthostatic SBP, DBP and pulse rate are assessed on Day 1 pre-dose, Day 1 2-hours post dose, Week 8/EOT (triplicate supine measurements approximately 1 minute apart [-3, -2, -1 minutes before standing] followed by a single standing measurement approximately 3 minutes after standing). Single resting measurements of SBP, DBP and pulse rate are measured on at Screening, Weeks 2, 4 and Week 10.

Orthostatic vital signs (SBP, DBP, pulse rate) will be derived for each subject as follows:

**Table 13 Derivation of Orthostatic Vital Signs**

Analysis Time point	Item	Derivation
Baseline, Treatment period	Average supine result	Average of the non-missing supine triplicates taken approximately 1 minute apart (-3, -2, and -1 minutes before standing).
Day 1 2-hours post dose, Week 8/EOT	Orthostatic result	Standing result – Average supine result.  If the result for standing or average supine is not available, then the result will be set to missing.

### **6.2.4 Electrocardiograms**

The 12-lead electrocardiograms (ECG) scheduled assessments will be made at Baseline, Week 8/EOT and Week 10. The results will be recorded as “normal”, “abnormal not clinically significant”, or “abnormal clinically significant”. Electrocardiogram variables are raw values (categorical) at each scheduled visit and changes from baseline (shift from baseline) at Week 8 and Week 10.

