## Safety and Tolerability Endpoints

- Treatment-emergent adverse events (AEs)/serious adverse events (SAEs) from Screening until EOS.
- Safety laboratory tests at Weeks 2, 4, 8 and 10
- Vital signs at Weeks 2, 4, 8 and 10.
- 12-lead ECG parameters at Weeks 8 and 10.
- Physical examination at Weeks 8 and 10.
- C-SSRS (evaluation of suicidal ideation and behavior) at Weeks 2, 4, 8 and 10.

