#### **5.4.5    Electrocardiogram**

A 12-lead ECG will be performed at Screening, Randomization, EOT and FU visits. All ECGs should be taken before any scheduled blood draws. ECGs will be recorded with the subject in the supine position, after the subject has been lying down for approximately 5 minutes. There should be at least 5 minutes between ECG measurements in case a repeat is needed. Any clinically significant adverse changes on the ECG will be reported as AEs. Printouts of all ECGs, marked with the subject number and initials, visit date and visit number should be stored in the subject's source data.

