#### **7.5.4    Electrocardiograms**

The shift table of the finding at baseline (normal, not clinically significant normal, clinically significant normal) to the worst finding during treatment period and follow-up period will be presented by treatment group.

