### **7.5.5 Electrocardiograms**

The baseline visit is the last measurement taken prior to the first dose of study drug.

The number and percentage of subjects with normal, not clinically significant abnormal, and clinically significant abnormal results as assessed by investigator for the 12-lead ECG will be tabulated by treatment group at each treatment visit and time point (Baseline, Week 8, EOT and Week 10).

Number and percent of subjects with 12-lead ECG abnormalities as well as number and percent of subjects whose 12-lead ECG reading changed from normal at baseline to abnormal will be tabulated by treatment group at each treatment visit and time point (Baseline, Week 8, EOT and Week 10)

A shift table of the finding at baseline ('normal', 'abnormal - not clinically significant' and 'abnormal - clinically significant') to the worst finding during the double-blind treatment period and follow-up period will be presented by treatment group.

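### The safety endpoint is 12-lead ECG parameters, but both documents analyse only a three-level investigator reading; no PR, QRS, QT or QTc variable is planned.

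*SAP*

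**What the plan says.** The protocol synopsis and section 2.3.1 include "12-lead ECG parameters at Weeks 8 and 10" among the safety and tolerability endpoints. Safety and tolerability is one of the two primary objectives.

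The analysis text is narrower in both documents:

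- **SAP 6.2.4, recording:** "The results will be recorded as “normal”, “abnormal not clinically significant”, or “abnormal clinically significant".
- **SAP 6.2.4, variables:** "Electrocardiogram variables are raw values (categorical) at each scheduled visit and changes from baseline (shift from baseline) at Week 8 and Week 10".
- **SAP 7.5.5:** the tabulation is of "The number and percentage of subjects with normal, not clinically significant abnormal, and clinically significant abnormal results as assessed by investigator for the 12-lead ECG". Counts of normal-to-abnormal changes and a worst-finding shift table are added. Table 31 sets windows for the categorical assessment only.
- **Protocol 7.5.4:** "The shift table of the finding at baseline (normal, not clinically significant normal, clinically significant normal) to the worst finding during treatment period". No other ECG analysis is planned there.

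On the source record, Protocol 5.4.5 says: "Printouts of all ECGs, marked with the subject number and initials, visit date and visit number should be stored in the subject's source data". Footnote j of the Schedule of Assessments specifies a single ECG per visit unless the investigator needs more for safety.

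**The concern.** An endpoint called ECG parameters would ordinarily mean measured quantities such as rate, PR, QRS and QT/QTc. The planned variable is instead a site-level judgement in three categories, made at up to about 35 sites with no central reading described. Such a reading can register a tracing that crosses an investigator's threshold for abnormality. It cannot yield a mean change in milliseconds, and it misses a shift that stays within the normal range.

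The other quantitative items in the same endpoint list are handled differently. Hematology, biochemistry and vital signs all get numeric values, change from baseline by arm and visit, and potentially clinically significant limits (SAP 7.5.3, 7.5.4, Table 23, Appendix 3). ECG gets none of these.

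At stake is whether the report can describe the endpoint it names. Multiple-dose experience before this trial was 14 days in healthy subjects; here patients are dosed for 8 weeks. The protocol itself mentions bradycardia with two GABA-B agonists and excludes a history of torsade de pointes or a family history of long QT syndrome, so ECG measurements are relevant on its own terms.

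**Working it through.** **1. Text comparison.** The documents give no ECG figure to reproduce, so the main check sets the text side by side.

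| Place | Quantity |
|---|---|
| Protocol synopsis and 2.3.1 | ECG parameters, Weeks 8 and 10 |
| Protocol 7.5.4 | Shift table of a categorical finding |
| SAP 6.2.4 | One three-level category and its shift |
| SAP 7.5.5 and Table 31 | Counts, normal-to-abnormal changes and worst-finding shift of that category |

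No unredacted text defines PR, QRS, QT, QTc or ECG-derived heart rate as a variable or sets an outlier limit for one. The mismatch is between the protocol's endpoint wording and the analysis sections of both documents.

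**2. Numbers available.** The synopsis plans 84 analysed subjects per arm. As a check, 2 × (1.645 + 0.842)² / 0.39² = 81.3, so 82 per arm. The stated 84 also allows for the futility analyses, so it is consistent. Then 84 / 0.95 = 88.4, so 89 per arm and 178 in total, as stated. A lower figure of 70 per arm is my assumption, to allow for missing Week 8 tracings.

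**3. Precision if intervals were recorded.** The half-width of a two-sided 90% confidence interval for the difference in mean change is 1.645 × SD × √(2/n). The SD of QTc change is an assumption.

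| Assumed SD (ms) | n = 84 per arm | n = 70 per arm |
|---|---|---|
| 12 | 3.0 | 3.3 |
| 15 | 3.8 | 4.2 |
| 20 | 5.1 | 5.6 |

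For example, 1.645 × 12 × √(2/84) = 3.0 and 1.645 × 20 × √(2/70) = 5.6. The three-level reading gives no corresponding estimate.

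**4. What the categorical table can show.** No safety test is planned, so power serves only as a gauge. With 84 per arm, one-sided 5%, a normal approximation (rough at such low rates) and assumed rates of abnormal readings, power is about 24% for 1% against 3%, 45% for 1% against 5%, and 82% for 1% against 10%. Only a large difference would be likely to show.

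**5. Usable time points.** Week 8/EOT is the only scheduled on-treatment ECG after baseline. The follow-up visit is 14 days after the last dose (Schedule of Assessments, footnote a). With the reported half-life of about 65 hours, 14 × 24 / 65 = 5.2 half-lives, so about 3% of the drug (0.5^5.2) would remain. Week 10 therefore says little about on-treatment effect.

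**The case against.** The strongest reply is that this is a wording mismatch in a trial not designed to measure intervals. Much of that stands.

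- **Heart rate is not missing.** A reader might infer that the trial has no numeric rate data. The documents do not support that. Pulse rate is summarised with change from baseline by arm at Day 1 (2 hours post-dose) and Weeks 2, 4, 8/EOT and 10, with outlier limits (SAP 6.2.3, 7.5.4, Table 23). Only ECG-derived rate is absent.
- **Interval values may be recoverable.** A reader might infer that no interval value exists. The printouts are kept as source and the eCRF is not among the documents. All that can be shown is that intervals are not planned as recorded or analysed variables.
- **The SAP does not depart from the protocol's analysis section.** It carries out the shift table of Protocol 7.5.4 and adds tabulations by visit.
- **ECG safety is not ignored.** Clinically significant adverse changes are reported as adverse events (Protocol 5.4.5), and treatment-emergent events are tabulated by arm.
- **Prior evidence is reassuring.** Protocol 1.2 reports no QTc effect and no exposure/QTc relationship in phase 1. It also reports steady state after about 9 days, and 70 mg single-dose exposure comparable to steady state at 30 mg daily.
- **The data would be limited.** There would be single tracings, no central reading, one scheduled on-treatment ECG, and no time relative to dose fixed in the ECG sections. The documents state no interval shift of concern against which 3.0 to 5.6 ms could be judged.

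These points limit the weight of the concern. They do not turn a three-level reading into an analysis of ECG parameters.

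**Conclusion.** The concern holds as a modest gap. The protocol names ECG parameters as a safety endpoint, while Protocol 7.5.4 and SAP 6.2.4 and 7.5.5 analyse only an investigator's three-level reading. What is lost is any estimate of a drug effect on PR, QRS or QT/QTc at Week 8.

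A reader might go further and conclude that the trial can say nothing about ECG safety, or that a cardiac signal is being overlooked. The documents support neither conclusion, given the pulse-rate analysis, the adverse event reporting and the phase 1 findings.

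The text comparison rests on no assumption. The half-width of about 3.0 to 5.6 ms rests on an assumed SD of 12 to 20 ms, 70 to 84 subjects per arm and a normal approximation. It illustrates what could be estimated and does not show that this precision is adequate.

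**What to change.** 1. In the eCRF, enter PR, QRS, QT and ECG heart rate from the single ECGs already taken at Randomization, Week 8/EOT and Week 10, and derive QTcF.
2. In Protocol 7.5.4 and SAP 6.2.4 and 7.5.5, add descriptive change-from-baseline summaries by arm, with no hypothesis test, in line with the rest of the safety analysis. Treat Week 8/EOT as the only scheduled on-treatment time point. Keep the shift table.
3. If intervals will not be captured, reword the endpoint in the synopsis and Protocol 2.3.1 as investigator ECG interpretation, so that the report does not imply that parameters were assessed.
4. In either case, correct the category labels in Protocol 7.5.4, which call both clinical-significance categories normal where the SAP calls them abnormal.

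No new ECG is needed. The cost is entering and checking several values per tracing at up to about 35 sites, plus a summary table. Single readings without central review will be noisier. The documents do not say whether the printouts carry machine-measured intervals. That should be confirmed first, since manual measurement would add work.
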